9.3. Informed Consent

A member of the responsible clinical team will briefly highlight the study to the patient and introduce a member of the local research team. They will approach the patient and explain the trial. In order to standardise the information provided to the patients, online and written recruitment materials will be made available to local research teams. The local research team will also be able to answer any additional questions that the patient might have.

This will then lead on to an informed consent discussion and if happy to proceed the patient will provide written electronic consent. Patients will be given as much time as possible to consider the information and discuss it with relatives/carers. Qualitative research in these emergency settings has shown that patients do not feel negatively affected by the relatively short time to make this consent decision. It will be clearly stated that the participant is free to withdraw from the study at any time for any reason without prejudice to future care, without affecting their legal rights, and with no obligation to give the reason for withdrawal.

Prospective consent will also be sought to access the participant's personal data within the various data warehouses in the UK that hold information on patients admitted to NHS hospitals. We will use these administrative databases to source additional data for the purposes described in this protocol. For participants treated in England we plan to use admitted patient care, emergency care, outpatient care and critical care datasets within the Hospital Episode Statistics (HES) database; in Scotland, The Scottish Morbidity Register – General/Acute Inpatient and Day Case (SMR01); in Northern Ireland the Acute Episode-based Activity Statistics (EAS); in Wales, the Patient Episode Database for Wales (PEDW) derived from the Admitted Patient Care dataset. Participants will be asked to consent to the sharing of their identifiable data (NHS number, date of birth, postcode and gender) and the trial ID with NHS Digital (or equivalent) in order to link to their record. NHS Digital (or equivalent) will then provide the University of Oxford with a pseudonymised dataset containing their personal data only identified with their trial ID number. The linkage file will be destroyed by the trusted third party once the linkage is complete.

Prior to any study related procedures or data being collected participants will complete the latest approved version of the consent form. The person who obtained the consent must be suitably qualified and experienced and have been authorised to do so by the Chief or Principal Investigator. Once completed, a PDF of the signed consent form will be automatically emailed to the participant. The local research team will be able to download a copy to place in the patient's medical notes. If the participant does not have access to email then a paper copy of their consent form will be provided by the local research team instead.

The consent form will include the link to the trial website so that participants will have access to all the trial information. If a participant does not have internet access a paper information sheet will be provided. The trial website will be maintained until the study archive period has reached completion. A subset of Informed Consent discussions at each site will be recorded, in order to monitor the consent process at recruiting sites and share good practice. A member of the research team will request verbal consent from the patient and the research associate before beginning the recording, and if the participant consents to recording, the discussion will begin with an oral recording of the request for consent to record, and the participant's agreement to the recording. It will be reiterated to the patients that providing consent to the recording of the consent process will not imply giving consent to participating in the trial.

9.4. Randomisation

Once informed consent has been given, the participant will be randomised by the local research team using a web-based service.

Allocations will be implemented as close as possible to the time of surgical decision-making once the participant has consented, whether this be in outpatient clinics or daily trauma meetings. Such a design most faithfully replicates real clinical practice so that the results of the trial will be as generalisable as possible to the wider NHS. This trial will test the two interventions as treatment pathways and hence be as pragmatic as possible.

The randomisation will be on a 1:1 basis, using a validated computer randomisation program managed through a secure (encrypted) web-based service by the Oxford Clinical Trials Research Unit, with a minimisation algorithm to ensure balanced allocation across the treatment groups, stratified by centre and fracture stability (defined as the presence of a posterior malleolus fracture). The minimisation algorithm will include a probabilistic element and a small number of participants randomised by simple randomisation at the start of the trial to seed the algorithm in order to ensure the unpredictability of treatment allocation.²⁷

Stratification by centre will help to ensure that any centre-effect will be equally distributed in the trial arms. While it is possible that the surgeons at one centre may be more expert in one or the other treatment than those at another centre, all of the recruiting hospitals have been/will be chosen on the basis that both techniques are currently routinely available at the centre i.e. theatre staff and surgeons will already be equally familiar with both forms of intervention. Similar to the findings from other trauma trials, we anticipate that each individual surgeon will only treat 2-3 participants enrolled in the trial, greatly reducing the risk of a surgeon-specific effect upon the outcome in any one centre. We will also incorporate centre as a random effect in the mixed effect primary analysis which takes into account any heterogeneity between centres. Stratification by fracture stability, specifically the presence or absence of a fracture of the posterior malleolus, will ensure that this important confounder is balanced between groups.

On randomisation of a participant the central trial office, main site contact and local study team will be notified. This will take place via an automated email as part of the randomisation process.

A paper-based randomisation system will be in place for use in emergencies, e.g. if the web-based randomisation service is not functioning, an event that is rare with this service.

9.5. Blinding

The primary outcome data will be collected from participants and entered directly onto the trial central database. It will not be possible to blind participants or those delivering the interventions.

The local research team reviewing hospital records will also not be blind to the treatment allocation. Any radiographs collected will be reviewed by an independent adjudication committee who, due to the presence of metalwork, will also not be able to perform their assessments blinded.

9.6. Description of study intervention, comparator and study procedures

Participants will be randomised to receive either surgical or non-surgical treatment. All treatments will be delivered under the supervision of a consultant trauma and orthopaedic surgeon.

9.6.1. Surgical treatment

Participants will undergo internal fixation of their fracture. The peri-operative care, for example pre-operative assessments, type of anaesthesia and the selection of antibiotics will be in accordance with local protocols. The selection of the operating position, the use of a tourniquet, approach, implants and surgical technique will be at the discretion of the treating surgeon. The specific technique and implants used by the treating surgeon will be recorded. Equally the application of any immobilising devices, such as cast or a walking boot, will also be recorded.

Participants' post-operative weight-bearing instructions will be left to the discretion of the treating surgeon, but all details will be recorded.

9.6.2. Non-surgical treatment

Participants will undergo close contact casting (CCC). Close contact casting is now an established intervention and is recommended as the primary treatment for adults over 60 years of age with unstable fractures in the current NICE guidance.⁶

In consultation with patients and patient representatives during the development of the trial protocol, and in common with the established practice for older adults based upon the non-surgical intervention tested in the AIM trial,³ all initial manipulations and applications of CCC will take place under anaesthesia.

The method of closed fracture manipulative reduction of deformity under image intensifier guidance will be left to individual surgeons and this falls within the common contemporary skills set of trauma and orthopaedic surgeons. The anaesthetic technique will be left to the discretion of the treating anaesthetist.

The CCC will be applied to the ankle once, in the opinion of the treating surgeon, the fracture has been adequately reduced. There will be standardisation of the casting materials, cast design and application, and moulding technique, as per the AIM trial training package.³ This technique will be revisited with clinical teams at each site with the FAME training team. In the event that an acceptable closed reduction cannot be achieved then the operating surgeon will proceed to open reduction and internal fixation (ORIF) if this is clinically appropriate. Conversion to ORIF in these circumstances, where an acceptable reduction cannot be achieved or maintained intraoperatively, will not constitute a protocol violation. Details of the reasons and the surgical technique used will be recorded.

Participants will be non-weight bearing for the duration of the CCC treatment.

The clinical follow-up schedule in the early phase will be left to the discretion of the treating surgeon. It is anticipated that some participants will require repeat applications of the CCC as the swelling around the injured ankle reduces. Subsequent applications of the CCC can be performed outside of an operating theatre, for example in plaster rooms. Advice regarding the frequency of clinical monitoring will be provided in the training sessions and rehabilitation booklet. After reapplications of the CCC repeat radiographs will be performed to confirm the reduction has been maintained.

9.6.3. Quality assurance of intervention

After discussion with patients, patient representatives and clinical experts during development of the protocol, intra-operative radiographs will be collected and assessed for technical adequacy of both interventions by an independent adjudication panel.

9.6.4. Ongoing treatment after test interventions

Clinical and radiographic monitoring of progress of both treatments will be at the discretion of the treating surgeon.

At the time a clinical decision is made to remove weight bearing and range of movement restrictions the rehabilitation materials will be delivered using standardised verbal and written and/or online instructions. A participant rehabilitation booklet has been prepared specifically for this study, with PPI input to ensure it is acceptable to participants. The booklet will be given to all participants as a printed, colour A4 booklet and may also be made available to participants online via the public website. The rehabilitation booklet includes the items below:

- a. Pain: Information to aid participant understanding of the condition and its management, to counter any misconceptions and pain management strategies (e.g. use of medication)
- b. Swelling: Advice on strategies to reduce swelling that include ice and elevation
- c. Stiffness: A core set of exercises that replicate normal physiological movements of the ankle and stretch the main muscle groups of the lower limb.
- d. Function: A core set of progressive strength exercises that target the main muscle groups of the lower limb and lower limb proprioceptive exercises.

Adhering to the TIDieR checklist for description and replication of rehabilitation interventions,²⁹ the initial rehabilitation intervention will be recorded on a rehabilitation CRF to capture the following information:

- Category of health care professional delivering the materials
- Grade/band of health care professional delivering the materials
- Where the materials were delivered (e.g. fracture clinic/ward/physiotherapy department)
- The duration of time (in minutes) to deliver the intervention

Training of providers will be undertaken at each site by the FAME training team in conjunction with the earlier described CCC training. Given the nature of clinical rotations that will occur on a regular basis and broader clinical team that may deliver the rehabilitation, each site will nominate a lead trainer who will be responsible for training of subsequent intervention providers. A rehabilitation booklet will be provided to the lead trainers by the trial team to standardise this process.

To increase participant adherence, there will be a further section describing the importance of recording progress and goal setting. Information will be provided on how to set goals using SMART principles. As part of this process they will be guided to include at least one of context, frequency, duration or intensity (e.g. encouraged to complete one set of exercises every day). In order to manage participant expectations of what is achievable there will be a final section informing participants of typical timescales when usual activities, such as driving, performing manual work, returning to sports, are usually resumed and points of contact if progress is not as expected.

The rehabilitation materials will only be delivered once and the time taken to deliver the intervention will be recorded on the CRF. The materials will not be tailored to the participant. Frequency and duration of exercises undertaken will be determined by the participant and they will be encouraged to record this in the relevant section of the participant rehabilitation booklet.

Further formal rehabilitation or adjunctive therapies will be left to the discretion of the treating clinician (e.g. referral to physiotherapy). Additional physiotherapy can take place in a number of settings outside of the immediate trial site; consequently this pathway will not be standardised and data will be self-reported by the participant at routine trial follow up. These data will include:

- a. Where they received the physiotherapy (community, home, hospital, private).
- b. Duration of the sessions.
- c. Number of sessions received.
- d. Method of delivery: face to face individual or group or remote telephone advice.

9.6.5. Quality assurance of standardised rehabilitation

Following site set-up the trial team will implement mechanisms to ensure treatment fidelity. This will be based on a standardised approach of evaluating fidelity:³⁰

- a) Direct Observations: With additional permissions, a member of the trial team will observe a subset of trial related procedures (permission will be sought from the trial participants to observe treatment sessions). An adherence evaluation form consisting of items that reflect the occurrence or non-occurrence of an event will form the basis of the assessment.
- b) Self Report: Alongside this, CRFs will be collected on intervention delivery including a Rehabilitation Delivery Form. This will be completed for every trial participant by site staff.

Points a) and b) will be evaluated annually for the duration of recruitment and intervention delivery. Any issues identified will be discussed by the Trial Management Group. If issues with individual sites are not resolved following the recommendations they will be escalated to the Trial Steering Committee.

9.7. Baseline Assessments

Participants will be asked to provide their contact details as well as the contact details of up to two alternative friends or family members. Experience from numerous orthopaedic trauma trials has highlighted that collection of these additional data reduces loss to follow-up substantially.

Baseline demographic data and retrospective pre-injury functional data using the OMAS instrument ²¹ and A-FORM²² will be collected. Participants will also be asked to complete the EuroQol EQ 5D-5L health-related quality-of-life questionnaire²⁴ to indicate their typical pre-injury health status.

9.8. Clinic Visit

Participants will usually attend at least one visit to the orthopaedic or trauma clinic after their initial treatment as part of standard care. During this visit, approximately 6 weeks post-treatment, the clinical team will perform a clinical assessment and standard radiographs will be taken. The research team will record any early complications that have occurred. The research team will transfer redacted radiographs taken intra-operatively and in the time since their index treatment to the central office, where they will be assessed by an independent adjudication committee.

9.9. Remote follow-up (8 weeks, 4 & 12 months and 2-5 years)

At 8 weeks, 4 months and 12 months after treatment, participants will be contacted by the central study office and invited to complete the OMAS, A-FORM, , EQ 5D-5L, patient reported experience (resource use and GRC) and WPAI questionnaires.

At 12 months participants will additionally be asked how they felt about being in the study in the Post-assessment questionnaire.

In a long-term follow-up, to be reported separately, at 2, 3, 4 and 5 years after treatment participants will be contacted by the central study office and invited to complete the OMAS, A-FORM, EQ 5D-5L, adverse events and GRC questionnaires.

The invitation will be sent to most participants via email and/or SMS, according to their stated preference. A secure online link will be included in the email or SMS so that participants can complete the questionnaires online.

Participants who do not complete the questionnaires within a specified time-frame will receive reminder emails and/or SMS and if this does not elicit a response, it will be followed up with a telephone call from the central study office. Exact timelines and frequency of phone calls will be specified in the data management plan.

9.10. Review of medical notes

At 12 months, the local research team at each centre will review hospital records for the trial participants and collect information on any visits and/or admissions related to the index fracture. These may include details of rehabilitation sessions offered at the treating centre and other outpatient care, including type of clinic visited and frequency, treating health care staff, and whether first appointment or routine follow-up; accident and emergency visits; and day-case and inpatient readmissions to hospital, reason for readmission, procedures and tests performed, and days admitted to various wards.

9.11. Early Discontinuation/Withdrawal of Participants

During the course of the trial a participant may choose to withdraw early from the study at any time, without giving reasons, and without prejudicing their clinical care.

Participants will **not** have the option to withdraw the data collected up until the point of withdrawal, as the data will be required for the intention-to-treat analysis and safety analysis. The options for withdrawal will be explained clearly in the Participant Information Sheet. The type of withdrawal and reason for withdrawal, if the participant is willing to provide one, will be recorded in the withdrawal CRF.

9.12. Definition of End of Study

The main analyses will be completed and reported after one year follow-up of the last participant. A planned long term follow-up study will be continued to the date of the last five year follow-up of the last participant. The end of study is defined as the 5-year follow-up of the last participant and once all queries have been resolved.

10. SAFETY REPORTING

This is a low risk, pragmatic trial where both of the trial interventions are in common use. In light of this, we do not anticipate many serious adverse events (SAEs) associated with either treatment. All adverse events will be reviewed by the local Principal Investigator and, submitted to the FAME central office if they fall into the SAE categories defined below.

10.1. Definition of Serious Adverse Events

A serious adverse event is any untoward medical occurrence that:

- · results in death
- is life-threatening
- requires inpatient hospitalisation or prolongation of existing hospitalisation
- results in persistent or significant disability/incapacity
- consists of a congenital anomaly or birth defect
- any other important medical condition which, although not included in the above, may require medical or surgical intervention to prevent one of the outcomes listed.

10.2. Reporting Procedures for Serious Adverse Events

For the purpose of safety recording for this trial, only unexpected serious adverse events (SAEs) potentially related to the intervention will be reported immediately to the Trial Team. When the local research team becomes aware of an unexpected SAE in a trial participant, the Principal Investigator (PI) will review the SAE locally and make a decision about the relatedness of the event to the intervention. If the PI assesses the SAE as potentially related and unexpected, the details of the event will be entered on an SAE reporting form on the database, and the research team will notify the trial team via email within 24 hours of the PI becoming aware of the event. Once received, causality and expectedness will be confirmed by the Chief Investigator or delegate. SAEs that are deemed to be unexpected and related to the trial will be notified to the Research Ethics Committee (REC) within 15 days. All such events will also be reported to the Trial Steering Committee and Data Monitoring Committee at their next meetings.

10.3. Reporting Procedures for Adverse Events not defined as serious

Adverse events that are unrelated to the intervention or treatment will not be reported.

Adverse events (AEs) that are foreseeable in the treatment of these fractures, and are not defined as SAEs, do not need to be reported immediately, provided they are recorded in the 'Complications' section of the Case Report Forms and/or Patient Questionnaires.

Other adverse events, foreseeable or unforeseeable, that are not in this list, will not be reported.

Foreseeable, related AEs include the following:

- (a) Related to CCC only:
- o loose cast or tight cast requiring reapplication
- failed closed reduction
- o pressure ulcer
- o plaster saw laceration
- (b) Related to surgical treatment only:
- o surgical site infection
- failed fixation
- o prominent implant
- wound dehiscence
- vascular injury

- (c) Related to both treatments:
- o revision surgery, defined as unplanned return to theatre
- symptomatic deep venous thrombosis
- o symptomatic pulmonary embolus
- o compartment syndrome
- o nerve palsy
- o complex regional pain syndrome
- pain/irritation/itchiness from cast

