6.3. Outcome measures

Table 1 describes the outcome measures being used in this trial.

Table 1: Objectives, outcome measures and time-points

Objectives	Outcome Measures	Time-point(s) of evaluation of this outcome measure
Primary Objective		
To determine whether functional outcomes at four months after treatment in people with unstable ankle fractures managed with close contact casting are not worse than those treated with surgical intervention.	Olerud-Molander Ankle Score (OMAS) ²¹	4 months

Socondary Objectives		
Secondary Objectives		
To quantify and draw inferences on observed differences in ankle function	OMAS ²¹	8 weeks, 12 months
between the trial treatment groups	Ankle fracture outcome of rehabilitation measure (A-FORM) ²²	8 weeks, 4 months, 12 months
during the first year after treatment.	Global rating of change question (GRC) ²³	8 weeks, 4 months, 12 months
2. To estimate differences in health-	EuroQol EQ-5D-5L ²⁴ health-related quality of	8 weeks, 4 months,
related quality of life between the trial	life instrument	12 months
treatment groups in the first 12 months post-treatment.	The Work Productivity and Activity Impairment Questionnaire (WPAI) 25	
3. To determine the risk of complications between the trial treatment groups in the first 12 months post-treatment.	Self-report questionnaires & medical notes: All potentially related adverse events including infection, symptomatic deep vein thrombosis, pulmonary embolus and unplanned return to theatre. Radiographs (routinely collected radiographs will be harvested):	8 weeks, 4 months, 12 months
	Fracture displacement, non-union, mal-union	
4. To estimate the resource use, costs and comparative cost effectiveness between the trial treatment groups at 12 months post-treatment.	Review of medical notes by research nurses at all trial centres complemented by bespoke resource use questionnaires administered to patients	6 weeks, 12 months,
5. To investigate the difference in ankle	Hospital Episode Statistics: inpatient,	
function, the risk of late adverse events and comparative cost effectiveness between the trial treatment groups within 5 years.	outpatient & emergency department databases OMAS ²¹	Annually until 5 years post-treatment
	A-FORM ²²	
	EQ-5D-5L ²⁴	
	Global rating of change question (GRC) ²³	
	Related adverse events from bespoke questionnaires administered to patients	

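### The protocol gives conflicting rules on which complications are recorded and by what route: Table 1, Section 10, 10.2 and 10.3 do not agree, and foreseeable serious events have no consistent path

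*Protocol*

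**What the plan says.** **Outcome definition.** Protocol Section 6.3, Table 1, sets the outcome for objective 3 (risk of complications in the first 12 months) as "All potentially related adverse events including infection, symptomatic deep vein thrombosis, pulmonary embolus and unplanned return to theatre". It adds fracture displacement, non-union and mal-union from routine radiographs. The sources are questionnaires and medical notes, with the same time-points for both arms.

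**Adverse-event list.** Section 10.3 introduces its list with "Foreseeable, related AEs include the following" and has three groups: four items under "Related to CCC only", five under "Related to surgical treatment only" and seven under both treatments. Events in the list are to be entered in the complications part of the CRF or in the patient questionnaire, provided they are not SAEs. For everything else the rule is "Other adverse events, foreseeable or unforeseeable, that are not in this list, will not be reported".

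**Serious events.** The opening of Section 10 has the local investigator review all adverse events, which are then "submitted to the FAME central office if they fall into the SAE categories defined below". Section 10.2 says that "only unexpected serious adverse events (SAEs) potentially related to the intervention will be reported immediately to the Trial Team". It promises the steering and monitoring committees only those SAEs judged both unexpected and related.

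**Treatment actually received.** Section 9.6.2 allows a participant allocated to casting to be converted to ORIF in theatre and does not count this as a violation. Section 9.6.1 foresees casts after surgery: "Equally the application of any immobilising devices, such as cast or a walking boot, will also be recorded".

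**The concern.** Avoiding the complications of surgery is the main advantage that Section 5.1 claims for casting, so objective 3 carries much of the argument for changing practice if non-inferiority is shown. The comparison depends on what sites write down, and no later analysis can restore an event that was never entered.

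Two things are at stake. The first is completeness of the outcome: a site that follows 10.3 literally would leave out events that Table 1 counts. The second is safety oversight: under Section 13.6 the DSMC reviews related SAEs that have been reported, and the text does not ensure that a foreseeable serious complication reaches it labelled as serious.

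**Working it through.** The plan states no figure on this point, so the check is to take each class of event and read off what each section requires.

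| Class of event | Section 10 opening | 10.2 | 10.3 | Table 1 |
|---|---|---|---|---|
| Serious, related, unexpected | to central office | immediate report | outside its scope | outcome |
| Serious, related, foreseeable | to central office | not covered (expected) | not covered (serious) | outcome |
| Serious, unrelated | to central office | not covered | not reported | not an outcome |
| Not serious, related, listed | not sent | not covered | complications form or questionnaire | outcome |
| Not serious, related, not listed | not sent | not covered | not reported | outcome |

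The first and fourth rows are consistent. The other three are not.

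**Row five: closed list against open outcome.** Table 1 asks for all potentially related events and names a few as examples. The opening of the 10.3 list uses *include*, which suggests an open list, but the closing sentence shuts it for foreseeable and unforeseeable events alike. Infection shows the mismatch: Table 1 names it without restriction, while 10.3 lists only surgical site infection, and only under surgery.

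**Row two: foreseeable serious events.** Section 10.3 is headed as covering events not defined as serious. Yet its third group includes pulmonary embolus, compartment syndrome and unplanned return to theatre, each of which can meet a criterion in 10.1 (life-threatening, or needing hospital admission or intervention). Such an event leaves 10.2 because it is expected and leaves the recording rule of 10.3 because it is serious. Only the opening sentence of Section 10 picks it up, and that sentence has no form, timing or onward route of its own.

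**Row three: scope of SAE submission.** The opening of Section 10 has no limit to related or unexpected events, whereas 10.2 has both limits. A site cannot tell which one governs.

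**The treatment headings.** Pressure ulcer, plaster saw laceration and loose or tight cast are tied to casting alone, but surgical participants may also be in a cast. Surgical site infection, wound dehiscence, failed fixation and prominent implant are tied to surgery alone, but casting participants may have had ORIF. The list is uneven on this itself: irritation from a cast is placed under both treatments, while other cast problems are not. Section 9.5 says that staff reviewing hospital records know the allocation, so labels of this kind could influence what they look for.

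**The case against.** The strongest reply is that Section 10 governs safety reporting while outcome data are collected under Table 1, the clinic visit (9.8) and the 12-month notes review (9.10). Those sections ask for any early complication and for fracture-related readmissions and procedures in all participants. The radiographic outcomes in Table 1 are absent from the 10.3 list, which suggests that the list does not limit outcome collection. Section 10.2 restricts only what is sent immediately, and Section 13.6 also gives the DSMC accruing data by treatment group.

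Much of this stands, and it limits the conclusion. It does not remove the conflict. Section 10.3 directs events to the complications form and the questionnaires, and questionnaires are a Table 1 source. The history in Section 23 describes the change to Section 10 as covering the complications to be collected. The closing sentence of 10.3 also omits the word *immediately*, which the section uses elsewhere. Nothing says that data by arm will mark foreseeable serious events as serious.

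A reader might go further and infer that complications are in fact ascertained differently in the two arms. The protocol does not show that. The headings attribute an event to a treatment; they do not say that an item is recorded only in the arm allocated to it. A surgical site infection after conversion is a listed event, and nothing bars its entry. The sources and time-points are common to both arms, and the CRF is not available to show otherwise.

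A reader might also try to size a bias by applying the surgical complication rates in Section 5.1 to converted participants. The protocol gives no conversion rate. The rates cite the trial in patients over 60, while Section 5.3 says that the risk in younger adults may be lower. Such a product would count events that fall under a label, not events that go unrecorded.

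**Conclusion.** The point holds as an internal conflict that should be resolved. Of the five classes of event set out above, three receive contradictory or incomplete instructions. Two of these, related unlisted events and foreseeable related serious events, bear directly on objective 3, and the second also bears on what the DSMC sees. This rests on the protocol text alone and needs no numerical assumption.

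The treatment-specific headings add a risk of unequal recording, given unblinded record review, permitted conversion and casts after surgery. Whether that risk is realised depends on the CRF and the Data Management Plan, which are not shown. No bias is demonstrated and no size can be given. The primary OMAS comparison is not affected.

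**What to change.** Three changes of wording, with a matching check of the CRF and questionnaire:

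1. Replace the closing sentence of 10.3 so that other potentially related events are also recorded, for example as free text, in line with Table 1.
2. State that the same complication items are recorded for every participant, whatever the allocation or the treatment received. If the treatment headings are kept, say that they describe attribution and do not restrict recording.
3. Reconcile the opening of Section 10 with 10.2 and 10.3. Say which SAEs go to the central office, and provide that foreseeable related events meeting the SAE definition are recorded, flagged serious and tabulated by arm for the DSMC, without expedited reporting.

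The cost is a protocol amendment, slightly more data entry and some coding of free text. Nothing in the clinical management of participants changes.
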